Title of Study: Exploring the Experience of Using a Prayer Mobile App

Date: 11/6/22

Study Protocol

Research Question:

What are the feasibility and preliminary effects of using Pray.com on spiritual well-being and mental health (stress, depressive and anxiety symptoms) in racial ethnic minority adults (i.e., individuals who identify as Black/African American, Latinx/Hispanic, Asian/Pacific Islander, Native American, or Multiracial)?

Hypothesis:

Individuals who use the Pray.com app will report that they are satisfied with the app, will use the app, and will report improved spiritual well-being and reductions in mental health indices (stress, depressive, and anxiety symptoms).

Outcomes:

Primary outcome: Feasibility (i.e., acceptability, demand, practicality)

Secondary outcomes: Spiritual well-being, satisfaction with life, religious commitment, racial/ethnic identity, stress, depression/anxiety

Measures:

Feasibility questions

- Acceptability (satisfaction, intent to continue use, perceived appropriateness, fit within culture)
- Demand (actual use, expressed interest, perceived demand)
- Practicality (ease or difficulty of use, ability to use app, cost analysis)

Well-being

Spiritual well-being scale (SWBS)

Satisfaction with life scale (SWLS)

Multi-ethnic identity measure (MEIM)

Religious commitment inventory (RCI)

Mental health

Perceived Stress Scale (PSS)

Hospital Anxiety and Depression Scale (HADS)

Miscellaneous items

Demographics

Sample size and inclusion criteria:

N = 75 (main study)

Subsample *n* = 15 (qualitative interviews)

Participants will be recruited through social media and various organizations that serve racial/ethnic minorities. Participants will be over the age of 18 and identify as a racial/ethnic minority (i.e., individuals who identify as Black/African American, Latinx/Hispanic, Asian/Pacific Islander, Native American, or Multiracial). Participants also must be willing to participate in a study that involves engaging in a regular Christian religious practice and are willing to download the Pray.com app.

Procedure:

Eligible participants will be given the Pray.com app and directed to use it daily. At the end of the study, a subsample of participants (N = 15) will be randomly asked to participate in an interview.

Participants will complete measures at baseline (i.e., time 1) and four-weeks (i.e., time 2). Participants will be compensated for their time completing surveys at baseline (\$15) and post (\$25) intervention for a total of \$40 at the end of the intervention. Participants who complete the qualitative interview portion of the study will receive an additional \$40. Participants who complete both surveys will also be entered in a drawing at the end of the intervention to win one of three \$99 gift cards. Finally, all participants will receive the Pray.com app for free for one year.

Statistical Analysis Plan

Quantitative feasibility data will be analyzed using descriptive statistics. Qualitative feasibility data will be analyzed using conventional content analysis. Data for the secondary outcomes will be analyzed using longitudinal multilevel modeling, exploring the effect of time on the dependent variables. We will also check for moderation with key variables (e.g., religious commitment, racial/ethnic identity). The main hypothesis is that participants will report high levels of acceptability, demand, and practicality after using the app.

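### Nothing in the eligibility criteria excludes people who already use Pray.com, and no listed measure records prior use, so the feasibility results can be inflated and the four-week change diluted

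*Combined protocol and SAP*

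**What the plan says.** All of the entry conditions are in the protocol section on sample size and inclusion criteria. "Participants will be over the age of 18 and identify as a racial/ethnic minority"; they must also be open to a study built on regular Christian practice, and must be people who "are willing to download the Pray.com app". No exclusion criteria are given. On sources, "Participants will be recruited through social media and various organizations that serve racial/ethnic minorities".

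The Procedure section adds: "Eligible participants will be given the Pray.com app and directed to use it daily". It also offers every participant a free year of the app.

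Feasibility is the primary outcome. Its components include satisfaction, intent to continue and actual use. The Statistical Analysis Plan summarises the quantitative feasibility data descriptively. It analyses the secondary outcomes by multilevel models "exploring the effect of time on the dependent variables", with two measurement times (baseline and four weeks) and no comparison arm. Religious commitment and racial/ethnic identity are given as examples of moderators. Prior use of Pray.com appears neither among the listed measures nor among those examples.

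**The concern.** The study has one arm and pools everyone, so the make-up of the sample feeds straight into both sets of results.

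- **Feasibility.** A current user has already tried the app and kept it. That person's satisfaction, intent to continue and use over four weeks say little about whether minority adults newly offered the app would take it up. The shift is likely to favour the main hypothesis of high acceptability, demand and practicality.
- **Secondary outcomes.** The time effect can be read as change after starting the app only if baseline comes before use. For an existing user it does not, so the contrast for that person is between two exposed time points.

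The two effects run in opposite directions: feasibility can look stronger and the changes in well-being and mental health can look weaker. Without a prior-use item, the sponsor could not show afterwards that the share of existing users was small.

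**Working it through.** **Step 1: does any condition bar an existing user?** Take each in turn.

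- Age and racial/ethnic identity: unrelated to app history.
- Openness to Christian practice: an existing user of a prayer app would be expected to meet it.
- Willingness to download: this is a disposition, not a history. Someone who has the app, or would reinstall it, can agree to it.
- Being given the app: this describes what the study does after enrolment and screens nobody out.

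An existing user can therefore be enrolled under the plan as written.

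**Step 2: the plan's own figure.** The only design figure is N = 75. No alpha, power, effect size, standard deviation or dropout rate is given, so it cannot be reproduced. Everything below is illustration on assumed inputs.

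**Step 3: dilution of the mean change.** Let q be the share of existing users (assumed 10%, 20%, 30%) and r their change as a fraction of the new-user change. The pooled mean change relative to new users is 1 − q(1 − r).

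- r = 0 (no further change, a pessimistic case): 1 − q = 0.90, 0.80, 0.70.
- r = 0.5 (daily use gives them half the change): 1 − 0.5q = 0.95, 0.90, 0.85.

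**Step 4: what that means at N = 75.** Assume two-sided alpha 0.05, 80% power, a paired normal approximation and an unchanged standard deviation of change. The detectable standardised change is (1.960 + 0.842)/√75 = 0.323. With r = 0, this effect becomes 0.323(1 − q), and power is Φ(2.802(1 − q) − 1.960):

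| q | diluted effect | power | N to restore 80% |
|---|---|---|---|
| 0% | 0.323 | 80% | 75 |
| 10% | 0.291 | 71% | 93 |
| 20% | 0.259 | 61% | 118 |
| 30% | 0.226 | 50% | 154 |

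The last column is 75/(1 − q)², rounded up.

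**Step 5: inflation of a feasibility proportion.** The pooled rate is (1 − q)·p_new + q·p_user, with both rates assumed.

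- 60% of new users and 95% of existing users satisfied: 63.5%, 67.0%, 70.5% at q = 10%, 20%, 30%.
- 60% and 90%: 63%, 66%, 69%.

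For scale, the sampling margin around 60% with 75 people is 1.96 × √(0.60 × 0.40/75) = 1.96 × 5.7 points, or about ±11 points.

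**The case against.** The strongest reply is that the wording points to newcomers. People who must be willing to download the app, and who are then given it free for a year, sound like people who do not have it. That is a fair reading of intent, but it is not a criterion that a recruiter could apply.

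Second, the research question concerns using the app, and app-naive adults are never named as the target. This stands in part: the sponsor may legitimately want a mixed population. But the hypothesis predicts improvement with use, and the analysis tests it as change from baseline. That is hard to interpret when baseline is already exposed.

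Third, the effects may be small. The assumed satisfaction shifts of 3.5 to 10.5 points lie inside the ±11-point sampling margin, no success threshold is stated for them to cross, and the secondary effects are called preliminary. This limits the consequence. Even so, composition bias is added to sampling error and does not shrink as the sample grows.

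Three stronger readings are tempting, and the documents do not support them:

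- A reader might infer that the results will be biased. That happens only if existing users enrol, and nothing shows that they will.
- A reader might infer that recruitment draws on the app's own audience. The stated sources are social media and organizations serving minorities, and the documents say nothing about who uses the app. That the free year might attract existing users is conjecture.
- A reader might infer that existing users could never be identified at analysis. The contents of the Miscellaneous items and Demographics entries and of the feasibility questions are not given, actual use is a demand component, and the moderator list is open-ended. A prior-use question may exist; the plan does not say so.

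**Conclusion.** The point holds in conditional form. The plan neither excludes current or recent Pray.com users nor states that prior use is recorded. If they enrol, the primary feasibility summaries can be inflated and the uncontrolled time effect diluted.

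The size cannot be determined from the documents. The 10–30% shares, the satisfaction rates and the zero-change case are all assumptions. On them, the mean change is 90–70% of the new-user change, and only 95–85% if existing users show half the new-user change. Zero further change is pessimistic because everyone is directed to daily use. The upward direction for feasibility is clearest for current users; someone who tried the app and stopped could rate it either way. The change is worth making because it is cheap and the information is hard to recover reliably after enrolment.

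**What to change.** Either of two changes would do.

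1. **Exclude.** Add a criterion that participants have not used the Pray.com app within a stated period before enrolment, checked by one screening question. Cost: one sentence and one question, and a few willing recruits turned away.
2. **Record and separate.** Add one baseline item on prior and current use of Pray.com. State in the Statistical Analysis Plan that the feasibility summaries and time-effect models will be reported in new users alongside the full sample. Cost: one item, one sentence and a somewhat smaller new-user analysis.

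The loss under the second option is modest. If 20% of the 75 were existing users, 60 new users would remain, and the margin around 60% would widen from about ±11.1 to 1.96 × √(0.24/60) = ±12.4 points. Under the Step 4 assumptions, power in those 60 is Φ(0.3235 × √60 − 1.960) = 71%, against 61% for the mixed 75 when existing users do not change.

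If the Miscellaneous items already contain a prior-use question, saying so and adding the analysis sentence is enough.

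### Do religious commitment and racial/ethnic identity, listed both as outcomes and as moderators with no wave or outcome list given, make the planned moderation analysis unsound?

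*Combined protocol and SAP*

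**What the plan says.** The Outcomes section makes feasibility primary and then lists "Secondary outcomes: Spiritual well-being, satisfaction with life, religious commitment, racial/ethnic identity, stress, depression/anxiety". Under Measures, the scales that match the two constructs at issue are the "Religious commitment inventory (RCI") and the "Multi-ethnic identity measure (MEIM"). The Procedure section states "Participants will complete measures at baseline (i.e., time 1) and four-weeks (i.e., time 2"), so each scale can supply two scores per participant. The sample is "N = 75 (main study"), and everyone receives the app.

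The Statistical Analysis Plan covers the secondary outcomes in two sentences. The first reads "Data for the secondary outcomes will be analyzed using longitudinal multilevel modeling, exploring the effect of time on the dependent variables". The second reads "We will also check for moderation with key variables (e.g., religious commitment, racial/ethnic identity"). It gives no wave, no outcomes to be moderated, no closed list, no significance level and no multiplicity rule. The Hypothesis section says that app users "will report improved spiritual well-being and reductions in mental health indices (stress, depressive, and anxiety symptoms") and names no moderator. The section closes with a main hypothesis that concerns feasibility only.

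**The concern.** A variable that is both an outcome and a moderator can enter the model in several ways. The moderator could be the time 1 score, the time 2 score or both, and it could be tested on the other outcomes or on its own change. These choices do not behave alike.

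A scale's baseline score is negatively correlated with its own change through measurement error alone, so testing a scale on itself will often produce a moderator where none exists. A time 2 score may already contain the participant's response to the app. With an open list of moderators the number of tests has no upper limit.

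At stake is whether a reported result, for instance that the app helps the more religiously committed most, could be believed, and whether a reader could tell that it was planned.

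**Working it through.** **Inputs.** From the documents: n = 75, two waves, one arm, two named moderators, six listed secondary outcomes. The documents give no significance level, correlation or dropout rate. Assumed here: two-sided 0.05, retest correlation r from 0.7 to 0.9, no true moderation, complete data. There is no figure in the plan to reproduce.

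**Form of the test.** Moderation is read as a moderator × time term. With two complete waves and a person-level moderator, this equals regressing change on the moderator. A check on one data set gave slope −0.0804 and t = −0.914 both ways.

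**1. A scale tested on its own change.** Take variance 1 at each wave. The covariance of the baseline score with change is r − 1, and the SD of change is √(2(1 − r)). The correlation is therefore −√((1 − r)/2). With Fisher's z and √(75 − 3) = 8.485, the rejection rate is about Φ(8.485·|z| − 1.96).

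| r | correlation | Fisher z (absolute) | 8.485·z | rate by formula | rate simulated |
|---|---|---|---|---|---|
| 0.9 | −0.224 | 0.227 | 1.93 | 49% | 49.2% |
| 0.8 | −0.316 | 0.327 | 2.78 | 79% | 79.7% |
| 0.7 | −0.387 | 0.409 | 3.47 | 93% | 93.9% |

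Simulated rates here and below use 20,000 studies per setting. The artefact is large, but it belongs to a test that the plan nowhere proposes.

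**2. A scale tested on another outcome, independent errors, no correlated change.** The other outcome's change is then only its own error difference, which is unrelated to the moderator at either wave. The expected correlation is 0. Simulated rates at r = 0.7 to 0.9 were 4.9% to 5.1% with the time 1 score and 5.1% to 5.3% with the time 2 score. The wave makes no difference.

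**3. The same, with same-survey errors correlated 0.3.** The correlation becomes −0.3·√((1 − r)/2) with the time 1 score and has the same size with opposite sign at time 2: 0.067, 0.095 and 0.116 at r = 0.9, 0.8 and 0.7. Simulated rates were 8.8%, 12.4% and 16.8% for time 1, and 8.5%, 13.4% and 16.7% for time 2. Both waves are inflated about equally, so naming time 1 would not cure this.

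**4. The same, with real individual changes (SD 0.5) correlated c across scales, independent errors.** The time 2 score then correlates with the other outcome's change by 0.25c / √(1.25·(0.25 + 2(1 − r))).
- c = 0.3, r = 0.7: 0.075 / √(1.25 × 0.85) = 0.073, rejection about 9.5%.
- c = 0.8, r = 0.9: 0.20 / √(1.25 × 0.45) = 0.267, rejection about 64%.

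The time 1 score stays at 4.7% to 5.1%. This is the only setting tried in which the wave changes the rate for cross pairs. Even here the time 2 test detects a real association between two changes. Calling that moderation by initial level would be a misreading, not a type I error in the usual sense. The SD of 0.5 and the values of c come from no document.

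**5. Number of tests.** Two moderators on the four outcomes that are not themselves moderators make 2 × 4 = 8 tests. Adding each moderator tested on the other makes 10. All 2 × 6 = 12 pairs include two self pairs. If depression and anxiety are scored separately, the 8 become 10 and the 12 become 14. For independent tests:
- 8 tests: 1 − 0.95⁸ = 33.7%
- 10 tests: 1 − 0.95¹⁰ = 40.1%

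Simulated values with time 1 scores and independent errors were 33% to 34% and 38% to 41%. With the two self pairs included, the family rate was 85% to 99.8%, driven by step 1. Fixing the wave and limiting the list to eight pairs leaves the 33.7% where it was.

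**The case for a change.** The best argument for amending the plan is that the text is silent on every point that matters here. The preceding sentence applies the models to all secondary outcomes, which include both moderators, so a literal reading does not exclude a self pair. The tests are never expressly labelled exploratory, nor is there a promise to report all of them. Three or four sentences would settle the matter with no new data. Even the favourable reading gives about a one-in-three chance of some spurious moderator, a figure that does not depend on the assumed retest correlations.

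The silence is real, and the arithmetic stands. What does not follow is that the plan is wrong. Failing to exclude a self pair is not the same as planning one, and treating a variable as moderator of its own change is not how the sentence would ordinarily be read. The one-in-three figure has nothing to do with the dual role or the wave, and specifying both would not reduce it. The wave argument also presumes that racial/ethnic identity means the MEIM score. The plan collects demographics too and recruits by self-identified group, so the category may be meant, in which case the wave question disappears for that moderator.

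**Conclusion.** The plan is incomplete on this point but is not shown to be biased, and no change is needed. The ordinary reading, a baseline score moderating change in the other outcomes, gives about 5% per test with independent errors, or 9% to 17% if same-survey errors correlate 0.3. In the latter case the choice of wave offers no protection. The alarming rates, 49% to 94% per test and 85% to 99.8% for the family, require self pairs that the documents do not propose. The 10% to 65% range for a time 2 score requires assumed correlated real changes and reflects an association that exists.

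The consequence is limited. Feasibility is primary and summarised descriptively, the effect of time is modelled separately and is untouched, and the moderation sentence commits only to a check, with no threshold and no confirmatory claim. With a single arm, any result would in any case describe who changed more over four weeks, not for whom the app worked. An analyst would naturally use the baseline score, leave out self pairs, and say in the report how many pairs were examined. All rates assume two-sided 0.05, n = 75 with complete data, and retest correlations of 0.7 to 0.9. None of these except the sample size is given in the documents.

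### Does the main hypothesis of high feasibility need a numerical benchmark and a stated denominator before the data are seen?

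*Combined protocol and SAP*

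**What the plan says.** Under Outcomes, the protocol names "Primary outcome: Feasibility (i.e., acceptability, demand, practicality") as primary. Under Measures it lists four sub-measures for the first domain, "Acceptability (satisfaction, intent to continue use, perceived appropriateness, fit within culture"), three for the second, "Demand (actual use, expressed interest, perceived demand"), and three for practicality, one of which is a cost analysis. The Hypothesis section predicts: "Individuals who use the Pray.com app will report that they are satisfied with the app, will use the app", followed by improvements in well-being and mental health.

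The Statistical Analysis Plan assigns the methods: "Quantitative feasibility data will be analyzed using descriptive statistics" and "Qualitative feasibility data will be analyzed using conventional content analysis". It closes with the main hypothesis: "The main hypothesis is that participants will report high levels of acceptability, demand, and practicality after using the app".

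On timing, the Procedure section says: "Participants will complete measures at baseline (i.e., time 1) and four-weeks (i.e., time 2"). Planned enrolment is 75, with 15 interviewed. There is no control group. The text gives no benchmark, interval, analysis set or dropout allowance.

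**The concern.** The hypothesis is directional and concerns the primary outcome, yet the plan never says what result would count against it. Four elements are unwritten: the level that counts as *high*, how 4 + 3 + 3 sub-measures become three domain results, whether an interval is given, and who is in the denominator.

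The denominator draws attention for two reasons. Compensation depends on completing surveys, so some non-completion is foreseeable. And the Hypothesis section speaks of people who use the app, which could be taken to leave non-users out.

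If these choices were made after seeing the data, the same answers could be reported as supporting feasibility or as falling short of it. What is at stake is an overstated feasibility conclusion. There is no treatment comparison to distort.

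**Working it through.** **Inputs.** From the documents: 75 enrolled; three domains with 4, 3 and 3 sub-measures; one survey after baseline, at four weeks. Assumed, because the documents give no such figures: 20% non-response (60 responders; 10% and 30% also shown), about 80% favourable answers, and a 70% benchmark (60% and 80% also shown). The plan gives no derivation of 75, so there is no planned figure to reproduce.

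**1. Denominator.** With r responders and x favourable, the share of all 75 lies between x/75 (no non-responder favourable) and (x + 75 − r)/75 (all favourable).

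| Responders | Favourable among responders | Range over all 75 |
|---|---|---|
| 68 | 54/68 = 79% | 54/75 = 72% to 61/75 = 81% |
| 60 | 48/60 = 80% | 48/75 = 64% to 63/75 = 84% |
| 52 | 42/52 = 81% | 42/75 = 56% to 65/75 = 87% |

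The uncertainty grows with non-response and its direction is unknown. Anyone given x, r and 75 can work it out.

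**2. Precision.** The Wilson 95% limits are [p + z²/(2n) ± z√(p(1−p)/n + z²/(4n²))] / (1 + z²/n), with z = 1.96. For 48/60, z² = 3.8416:

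- centre: (0.8 + 0.0320)/1.0640 = 0.782
- half-width: 1.96 × √(0.002667 + 0.000267)/1.0640 = 0.100
- interval: 68.2% to 88.2%

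The same formula gives 52.7% to 73.9% for 48/75.

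**3. Which results are ambiguous.** At n = 60, using the interval as the criterion:

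| Assumed benchmark | Interval wholly below, up to | Inconclusive | Interval wholly above, from |
|---|---|---|---|
| 60% | 28/60 (47%) | 29 to 43 | 44/60 (73%) |
| 70% | 35/60 (58%) | 36 to 48 | 49/60 (82%) |
| 80% | 41/60 (68%) | 42 to 54 | 55/60 (92%) |

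Fewer than half favourable falls below all three benchmarks (at most 28/60 for the lowest), and 55/60 or more exceeds all three. The missing benchmark matters in between.

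**4. Does one data set give three verdicts?** It might be said that 48 favourable of 60 is above 70% (80%), inconclusive (68.2% to 88.2%) and below it (48/75 = 64%). That mixes criteria. By point estimate there are two verdicts, and the second uses a worst-case bound. By interval, 48/60 and 48/75 both include 70%, so both are inconclusive.

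**5. What a formal rule would do.** Require the interval to lie above 70% in every domain, that is, at least 49/60 in each. With X binomial(60, π), one domain is met with probability P(X ≥ 49):

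- π = 0.80: 0.449 for one domain; 0.449³ = 0.09 for all three if independent; at most 0.45 if fully correlated.
- π = 0.85: 0.819 for one domain; 0.819³ = 0.55 for all three if independent; at most 0.82.

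At this sample size, an app that four in five people liked would usually fail such a rule.

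**The case for a change.** The strongest case for a change is that the plan need not have stated a directional hypothesis but did. A benchmark per domain, or rewording the sentence as a descriptive aim, costs only a few words. The missing value for *high* remains even with complete follow-up. The combining rule also matters. Suppose each item has a true favourable rate of 65%, and an item passes at an observed 70% or more (53/75). One item then passes with probability 0.183. With four independent acceptability items, at least one passes with probability 1 − (1 − 0.183)⁴ = 55.4%, and all four pass with probability 0.183⁴ = 0.1%. Real items correlate, which narrows that gap without closing it.

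What stands is that the definitions are unwritten and that middling results could be described generously. Neither redaction nor text extraction explains this.

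What does not stand is that this makes the analysis wrong. The plan sets no pass mark, so no pass mark can be misapplied. Any benchmark would have to be the sponsor's own choice, since nothing in the documents supplies one. Intervals, retention and a column over all enrolled are good reporting that a descriptive analysis already allows. The worry that a users-only denominator makes demand true by definition is strained: the Statistical Analysis Plan speaks of participants, everyone eligible is given the app, and actual use can mean amount of use, which varies even among users.

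**Conclusion.** No change to the plan follows. This is missing detail of a kind analysts fill sensibly: tabulate each sub-measure, give the number of responders beside the 75 enrolled, and describe the level observed. The main hypothesis then reads as an expectation for an exploratory one-group study, and its descriptive primary analysis suits that design.

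The size of what is left open depends on assumptions. At 20% non-response and 80% favourable among responders, the share of all enrolled could be 64% to 84%. Against a 70% benchmark at n = 60, counts of 36 to 48 would be inconclusive. Results outside the middle range would read the same under any sensible definition. A strict rule over three domains would be met only 9% to 45% of the time at a true rate of 80%, depending on how the domains correlate, so formality would not clearly improve the conclusion. A reader of the results should treat a claim of *high* feasibility as a description of the observed levels and not as a passed test.
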